5.4.6 Adverse Events Reporting Timeline

Life-threatening or fatal unexpected adverse events associated with the use of the study drug or procedures must be reported to the IRB within 24 hours of discovery of the incident with subsequent follow-up submission of a detailed written report.

The FDA must be notified by telephone or facsimile transmission of a human adverse event that is fatal or life-threatening no later than 7 calendar days after receiving the respective human adverse event information, followed by the subsequent submission of a written IND Safety Report.

Serious and unexpected adverse events associated with the use of the study drug or procedures must be reported to the IRB with subsequent follow-up submission of a detailed written report in accordance with the respective policies and procedures of the IRB. Written IND Safety Reports will be submitted to the FDA as soon as possible and, in no event, later than 15 calendar days following the investigator-sponsor's receipt of the respective adverse event information.

A summary report of the findings will be prepared and submitted to the regulatory agencies.

5.5 RISKS MANAGEMENT PROCEDURES

5.5.1 Protection Against Risks

General Risks of Study Protocol and Procedures

All research interventions/activities will be conducted in private patient care areas. The collection of sensitive information about subjects is limited to the amount necessary to achieve the aims of the research, so that no unneeded sensitive information is being collected.

All demographic and clinical information about the subject will be stored on an electronic password-guarded study database under the supervision of the Investigator for this protocol. The electronic database that is being used for the purpose of this study has not been fully validated to be in compliance with the FDA regulations at 21 CFR Part 11; i.e. taking into account the limited scope of this clinical investigation. The data will be stripped of individual identifiers and stored anonymously with a subject number. Information linking subject identifiers with the coded subject number will be stored under password protection on computers in locked areas, with access only to the database manager. Maintaining records in locked files in locked offices will protect confidentiality of subjects. All staff will sign confidentiality statements. Access to the database will be limited to the data manager and staff under the supervision of the Investigator.

Specimens will be stripped of subject identifiers and stored according to a similar coding protocol as described above. These specimens will be stored safely in the custody of the Investigator responsible for the individual assays. The Investigators will limit future access to any remaining sample to only those investigators with prior IRB approval for their studies.

All staff involved in this study are properly credentialed and instructed in the areas of testing, confidentiality, and safety.

The Investigator will retain the data for the entire period of this study. The Investigator may continue to use and disclose subjects' de-identified information for the purpose of this study for a minimum of seven years after final reporting or publication of the study. If the subject and/or legal representative decide to withdraw or be withdrawn from study participation, they may request that the study data and samples be destroyed.

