
Study Design:
	
The study aims to assess the safety and feasibility of oral nitrite in adults with HFrEF, HFpEF or healthy control.
 
Subjects who meet the Inclusion Criteria and none of the Exclusion Criteria will receive oral sodium nitrite for 4 weeks. We will stratify dosing as below:
 
Study drug to be initiated and prescribed as below:
 
 a. 20 mg tid to subjects who 
 i. are \geq80 years of age or, ii. are age 70 to <80 years with recent history of low blood pressure or other factors that PI judges to be at higher risk for hypotensive response b. 40 mg tid to subjects who 
 i. are age 70 to <80 with no recent history of low blood pressures or PI judges to be at lower risk for hypotensive response c. Subjects to ingest drug once in the morning and again in the early afternoon and again in the evening, approximately 6 hours apart.

	
Subjects will be evaluated as outpatients with the first dose of study drug. Blood pressure, heart rate, methemoglobin levels and plasma nitrite will be measured in the first two hours after dosing. Every week safety visits will occur by phone to assess symptoms, adverse events (AE), interval histories and medication compliance review.
 
Subjects will also be contacted by the study investigator and/or the study coordinator by phone for a follow-up assessment one week following completion of Visit 5.

Planned Sample Size:	30 subjects
Duration of Treatment:	4 weeks

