Any event meeting #1 or #2 above will be reported immediately to the IRB in their required format. In the event that a participant either withdraws from the study or the PIs decide to discontinue a participant due to a SAE, the participant will be monitored by the co-PIs until (a) a resolution is reached (e.g., the problem has resolved or stabilized with no further change expected), (b) the SAE is determined to be clearly unrelated to the study intervention, or (c) the SAE results in death. Outcomes of SAEs will be regularly reported to the IRB. A summary of the SAEs that occurred during the previous year will be included in the annual progress report as well as in the annual IRB renewal. Suicidal ideation and AEs will be formally assessed immediately after treatment and referrals for further care will be made as needed. In the Informed Consent Form, we will provide specific information about emergency contacts. Participants are instructed to contact [name] during working hours. After hours participants will be provided the information on how to contact the cardiology fellow on call.

Stopping Rule:

For safety reasons, we propose to discontinue participation for any subject who experiences *any of the following*:

1. Methemoglobin greater than 5% after dose lowering
A nitrite dose reduction is proposed from 40 mg three times daily to 20 mg three times daily if this methemoglobin % is reached at any study interim visit, as described in section 2.2.6 (phone report of change in skin tone and dizziness or other symptom suggestive of methemoglobinemia). Follow up symptom assessment for 48 hours and repeat methemoglobin in 3 days will be implemented. If methemoglobin is greater than 5% on the lower nitrite dose, participation in the study for the subject will be discontinued.
2. Blood pressure drop after dose lowering
Blood pressure and related symptoms.

If subjects experience lightheadedness or dizziness after visit 3 while they are on the drug, we request that they call the study coordinator who will inventory their symptoms, compare to baseline (measured at pK) levels, and discuss need for interim visit with study physician. If a visit is indicated, we will measure blood pressure, RR, heart rate, and check methemoglobin level by a finger probe. A study physician will evaluate each subject, including:

- a. review of all clinical measures,
- b. subject history of symptoms,

c. blood pressures pre- and while on drug.

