5.4.3 Parameters to be monitored

The following progress will be monitored throughout the course of the research to ensure the safety of subjects as well as the integrity and confidentiality of their data.

- An evaluation of the progress of the research study, including subject recruitment and retention, and an assessment of the timeliness and quality of the data.
- A review of collected data (including adverse events, unanticipated problems, and subject withdrawals) to determine whether there is a change to the anticipated benefit-to-risk assessment of study participation and whether the study should continue as originally designed, should be changed, or should be terminated.
- An assessment of external factors or relevant information (e.g., pertinent scientific literature reports or therapeutic development, results of related studies) that may have an impact on the safety and study participants or the ethics of the research study.
- A review of study procedures designed to protect the privacy of the research subjects and the confidentiality of their research data.

The severity of adverse changes in physical signs or symptoms will be classified as follows:

- Grade 1 (Mild): asymptomatic or mild symptoms; clinical or diagnostic observation only; intervention not indicated.
- Grade 2 (Moderate): minimal, local or noninvasive intervention indicated; limiting age-appropriate ADL (Activities of Daily Living).
- Grade 3 (Severe): medically significant but not immediately life-threatening; hospitalization or prolongation of hospitalization indicated; disabling; limiting self care ADL.
- Grade 4 (Life-threatening): consequences; urgent intervention indicated.
- Grade 5 (Death): event is a direct cause of death.

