5.4.4 Frequency of Monitoring

The Investigator will review subject safety data as it is generated. The Investigator, sub-investigators, and the research staff will meet on a two week interval to re-evaluate study goals, subject recruitment, data coding and retention, documentation and identification of adverse events, complaints and confidentiality of subjects. There will be an evaluation of the progress of the research study, including assessments of data quality, time lines, participant recruitment, accrual, and retention. The Investigator will also review the outcome and adverse event data to determine whether there is any change to the anticipated benefit-to-risk ratio of study participation and whether the study should continue as originally designed or should it be re-evaluated and changed.

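### Section 5.5.1 lets a withdrawn subject ask for study data, not only samples, to be destroyed, with no exception for adverse events already recorded

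*Combined protocol and SAP*

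**What the plan says.** Section 5.5.1 (Protection Against Risks) makes three statements in one paragraph.

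- On retention during the study: "The Investigator will retain the data for the entire period of this study".
- On later use: the investigator may go on using de-identified information "for a minimum of seven years after final reporting or publication of the study". This is worded as a permission.
- On withdrawal: "If the subject and/or legal representative decide to withdraw or be withdrawn from study participation", then "they may request that the study data and samples be destroyed".

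The withdrawal sentence covers subjects who leave by choice and subjects whom the investigator takes off study. It names data as well as samples. No section says how a request is decided, or that adverse events or other data recorded before withdrawal are kept.

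Other sections rely on those records. The Study Design entry of the synopsis says: "The study aims to assess the safety and feasibility of oral nitrite". Section 5.4.3 lists among the items to be monitored: "A review of collected data (including adverse events, unanticipated problems, and subject withdrawals"), as a basis for deciding whether the study continues, changes or ends. Section 5.4.4 adds: "The Investigator will also review the outcome and adverse event data", again to judge benefit against risk. Section 5.4.1 says: "A summary of the SAEs that occurred during the previous year will be included in the annual progress report".

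**The concern.** Sections 2.2.6 and 5.4.1 foresee stopping treatment for blood-pressure symptoms or for methemoglobin that stays above 5%. They note that subjects who started on 20 mg may have to be withdrawn because no lower dose is available. Subjects stopped for harm are therefore among those who gain the right to have their data destroyed. Subjects who complete treatment are not offered it.

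If the right is used, the record leaves both the numerator and the denominator of any safety tabulation, and it does not leave at random. In a trial of 30 subjects, where safety is a stated aim and the results are meant to inform a larger trial, a few such deletions could make the drug look better tolerated than it was.

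**Working it through.** The point is textual, so the main check sets the clauses side by side. The arithmetic only shows scale.

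**1. Which events are held outside the study file?**

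| Route | What it covers | Section |
|---|---|---|
| Immediate IRB report | Unexpected, related or possibly related events that are serious or point to greater risk | 5.4.1 |
| Annual SAE summary and SAE outcomes to the IRB | Serious events | 5.4.1 |
| FDA notification and IND safety reports | Fatal or life-threatening events; serious and unexpected events | 5.4.6 |
| Adverse event case report form | Clinically important events that are unexpected or study-related | 5.4.5 |

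The first three routes put a copy outside the study file. The fourth is part of it. Section 5.1.1 lists hypotension in heart-failure subjects as frequent, so it is expected. A non-serious episode of that kind need not enter any of the first three routes, even if it leads to withdrawal. It may then exist only in records that Section 5.5.1 allows the subject to ask to have destroyed.

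**2. Group size.** The documents give 30 subjects in three groups but not the split. Section 2.5 states detectable changes of 32 within a group and 42 between groups (SD 32, 80% power, two-sided 0.05). I tested n = 10 per group with the noncentral t distribution:

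- Within group: power = P(T > t(0.975, n−1)), with noncentrality δ√n/32. Power of 80% is reached at δ = 31.87 (stated 32; power at 32 is 80.3%).
- Between groups: 2n−2 degrees of freedom, noncentrality δ/(32√(2/n)). Power of 80% is reached at δ = 42.40 (stated 42; power at 42 is 79.3%).

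Ten per group reproduces the plan's figures, so it is a reasonable assumption. The concern does not depend on it.

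**3. Effect of deleting records in one group of 10.** Destroying d of x cases changes the rate from x/n to (x−d)/(n−d).

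- x = 2, d = 1: 2/10 = 20% becomes 1/9 = 11.1%.
- x = 1, d = 1: 1/10 = 10% becomes 0/9 = 0%.

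**4. Effect in both heart-failure groups together (assumed 20).** This is the extreme case: every affected subject withdraws, asks for destruction and has it granted. Intervals are Clopper-Pearson 95%. With zero events in m subjects the upper limit is 1 − 0.025^(1/m).

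| Cases | Records kept | All case records destroyed |
|---|---|---|
| 1 | 1/20 = 5% (0.1 to 24.9%) | 0/19, upper limit 17.6% |
| 3 | 3/20 = 15% (3.2 to 37.9%) | 0/17, upper limit 19.5% |
| 5 | 5/20 = 25% (8.7 to 49.1%) | 0/15, upper limit 21.8% |

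In the last row the rate actually seen, 25%, lies above the upper limit that would be reported after deletion.

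**The case against.** The strongest reply is that the paragraph contains no contradiction. It states a general retention rule and then a specific provision for withdrawal, which reads naturally as rule plus exception. The sentence also gives a right to ask; it does not promise that the request is granted. Both points stand, and I do not call the paragraph self-contradictory. But the text sets no limit on the request, and reading it as an intended exception leaves open what happens to the events that the safety review needs.

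A second reply is that safety is handled as it happens. Under Section 5.4.1, staff report all adverse events to a principal investigator at once, and subjects who leave because of a serious event are followed to resolution. Under Section 5.4.4 the investigator reviews safety data on an ongoing basis and the team meets every two weeks. This also stands. A reader might infer that the review and reporting duties become impossible once a record is destroyed. The documents do not support that, because review and qualifying reports would usually come before the request. What remains exposed is the final dataset, for non-serious, expected events.

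Three further inferences are tempting and should not be drawn.

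- *That deletion would remove the evidence for stratified dosing.* The responses of the three heart-failure subjects are already written into Sections 2.2.2 and 5.1.1, and nothing says that any of them withdrew.
- *That the mixed models would lose first-dose data.* The time factor in Section 2.5 has two levels, baseline and 4 weeks, so post-dose Visit 3 values are not a level of it. A subject who leaves before the 4-week tests has no change score whether or not the record is kept, so the loss of power belongs mostly to dropout.
- *That drug accountability records would go.* Section 2.2.6 describes logs of drug dispensed and returned. Nothing shows that these are the study data meant in Section 5.5.1.

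Finally, how far withdrawing subjects control their data is partly a question of participant rights under IRB oversight, and the consent pages are not in the review copy. They may already limit what is destroyed.

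**Conclusion.** The concern holds in a limited form. As written, Section 5.5.1 allows non-serious, expected adverse events, notably hypotension in heart-failure subjects, to be removed on request from the study dataset. Those eligible to ask include subjects stopped for poor tolerance. This weakens the stated safety aim and any later summary of adverse events and withdrawals. It does not undo reports already made to the IRB or FDA.

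The size is unknown. A loss needs a withdrawal for harm, a request, its acceptance, and an event not already reported elsewhere. The documents give no rate for any of these. Harm is also not the only ground for stopping: biopsy refusal and poor compliance are listed in Section 5.4.1. Section 2.5 plans no hypotension rate by group, so the figures above (2/10 to 1/9; 3/20 to 0/17) illustrate sensitivity in small groups and are not forecasts. They rest on the assumed 10 per group and on invented case counts.

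The change is still worth making because the possible loss is selective and can be prevented cheaply by altering a stated rule.

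**What to change.** For subjects consented from now on, replace the last sentence of the retention paragraph in Section 5.5.1 with wording such as:

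*On withdrawal, remaining stored samples will be destroyed at the subject's request and neither samples nor data will be put to future use. Data obtained up to withdrawal, at least exposure, adverse events and the reason for withdrawal, will be kept in coded form and included in the safety summary and analysis.*

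Then:

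1. Check that the consent wording agrees, and amend it if it does not.
2. Honour the existing right of subjects already consented.
3. Report the number of records destroyed, by group, with the safety results, so that readers can see which denominators are affected.

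The cost is a short protocol change, any matching consent text and IRB review. The downside is a narrower option for withdrawing subjects, who keep the right to have stored samples destroyed.

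The change cannot reach everyone. Sections 2.2.2 and 5.1.1 record 10 controls and 3 heart-failure subjects already enrolled, so at most 30 − 13 = 17 subjects would come under the new wording. If the groups are 10 each, all 17 would be heart-failure subjects (20 − 3), the population in which hypotension is listed as frequent.

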5.5.2 Protection Against Potential Risks of Experimental Intervention

- Involvement by trained staff / investigators with experience in the administration of the study drug
- Continuous monitoring by the Data and Safety Monitoring Board
- Required Education in the Protection of Human Research Participants

The Investigator and all sub-investigators listed on University of Pittsburgh Institutional Review Board approved protocol are required to participate in a course entitled The Education and Certification Program in Research & Practice Fundamentals (RPF). This web based tutorial is a requirement of the IRB for protocol submission.

6. COSTS AND PAYMENTS

6.1 COSTS

Study drug and all research testing will be supported by ongoing research grants. All medications, lab tests, and any procedures described will not be billed to the subjects and/or their health insurance company.

6.2 PAYMENTS

Subjects will be reimbursed \$200 for the baseline study visits after completion of Visit 3 [Visits 1 (\$50), Visit 2 (\$75) and Visit 3 (\$75)]. Subjects will be reimbursed an additional \$370 following the completion of Visit 5 [Visit 4 (\$125), Visit 5 (\$145) and Study drug compensation (\$100)]. The total compensation will be \$570.00 and will be paid via the University's WePay debit card system. Subjects will also be provided a voucher for outpatient UPMC Montefiore parking at all visits. In the event that a subject drops out due to an AE, the subject will be reimbursed for the individual study visits that they completed to date per the above reimbursement schedule.

7.2 SOURCES OF SUPPORT

2014 Mitochondria, Aging and Metabolism/Basic Biology Aging Pilot Project Program

